**Protocol Revision History**

Initial Approval Version	09/02/2020
Amendment #1	09/08/2020
Amendment #2	11/09/2020 (not submitted)
Amendment #3	12/07/2020
Amendment #4	01/11/2021
Amendment #5	03/29/2021 (submitted, not approved)
Amendment #5	05/21/2021
Amendment #6	09/01/2021
Amendment #7	07/05/2022
Amendment #8	04/11/2023
Amendment #9	06/09/2023

## **STATEMENT OF COMPLIANCE**

The trial will be carried out in accordance with International Conference on Harmonisation Good Clinical Practice (ICH GCP) and the following:

- United States (US) Code of Federal Regulations (CFR) applicable to clinical studies (45 CFR Part 46, 21 CFR Part 50, 21 CFR Part 56, 21 CFR Part 312, and/or 21 CFR Part 812)

National Institutes of Health (NIH)-funded investigators and clinical trial site staff who are responsible for the conduct, management, or oversight of NIH-funded clinical trials have completed Human Subjects Protection and ICH GCP Training.

The protocol, informed consent form(s), recruitment materials, and all participant materials will be submitted to the Institutional Review Board (IRB) for review and approval. Approval of both the protocol and the consent form must be obtained before any participant is enrolled. Any amendment to the protocol will require review and approval by the IRB before the changes are implemented to the study. In addition, all changes to the consent form will be IRB-approved; a determination will be made regarding whether a new consent needs to be obtained from participants who provided consent, using a previously approved consent form.

## Glossary of Abbreviations

AE	Adverse event
AIDS	Acquired immune deficiency syndrome
ATC	Advanced Technology Consortium
BJH	Barnes Jewish Hospital
CBC	Complete blood count
CD4+	Cluster of differentiation 4+
CFR	Code of Federal Regulations
CMP	Comprehensive metabolic panel
CONSORT	Consolidated Standards of Reporting Trials
CRF	Case report form
CT	Computed tomography
CTCAE	Common Terminology Criteria for Adverse Events
CTEP	Cancer Therapy Evaluation Program
CYP3A4	Cytochrome P450 3A4
DHHS	Department of Health and Human Services
DNA	deoxyribonucleic acid
DOB	Date of birth
DSM	Data and Safety Monitoring
ECOG	Eastern Cooperative Oncology Group
EDTA	ethylenediaminetetraacetic acid
FWA	Federal wide assurance
GCP	Good Clinical Practice
GTV	Gross Tumor Volume
HHS	Department of Health and Human Services
HIV	Human Immunodeficiency Virus
HRPO	Human Research Protection Office (IRB)
ICH	International Council for Harmonisation
IGRT	Image-guided radiation therapy
IMRT	Intensity modulated radiotherapy
IL	Interleukins
IRB	Institutional Review Board
MRI	Magnetic resonance imaging
NCCN	National Cancer Center Network
NCI	National Cancer Institute
NIH	National Institutes of Health
NRS	Numeric Rating Scale
NSCLC	Non-small cell lung cancer
OAR	Organs at risk
OHRP	Office of Human Research Protections
PD-L1	Programmed death ligand 1

PI	Principal investigator
PRO-CTCAE	Patient Reported Outcomes-Common Terminology Criteria for Adverse Events
PTV	Planning Target Volume
QASMC	Quality Assurance and Safety Monitoring Committee
QoL	Quality of Life
RNA	Ribonucleic acid
SAE	Serious adverse event
SCC	Siteman Cancer Center
SBRT	Stereotactic body radiation
SFRT	Spatially fractionated radiotherapy
Lattice SBRT	Spatially-fractionated stereotactic body radiation
SIB	Simultaneous integrated boost
SLCH	St. Louis Children's Hospital
TEAE	Treatment emergent severe adverse events
TNF	Tumor necrosis factor
TPCF	Tissue Procurement Core Facility
UPN	Unique patient number
VMAT	Volumetric modulated arc therapy
WU	Washington University

## PROTOCOL SUMMARY

Title:	A Trial of Palliative Lattice Stereotactic Body Radiotherapy (SBRT) for Patients with Sarcoma, Thoracic, Abdominal, and Pelvic Cancers
Study Description:	Lattice SBRT will be used to deliver palliative radiotherapy to large ( $\geq 4.5$ cm) tumors for patients with soft tissue sarcomas, thoracic cancers (including esophageal), abdominal, and pelvic cancers. The safety and efficacy of this approach will be assessed.
Objectives:	
Primary Objective:
 
 
1. To evaluate the efficacy and safety of 5-fraction palliative Lattice SBRT in patients with large lesions (<math>\geq 4.5</math> cm) who are planning to undergo palliative radiotherapy. This will be assessed with the co-primary endpoints of target lesion control at 6 months and rate of treatment-related severe toxicity within 6 months.
 
 
Secondary Objectives:
 
 
1. To assess the rate of treatment-related severe toxicity within 12 months of completion of treatment (i.e. late toxicity)
 
2. To assess patient reported toxicity with PRO-CTCAE
 
3. To assess patient-reported QoL with PROMIS
 
4. To assess patient-reported pain
 
 
Exploratory Objectives:
 
 
5. To evaluate blood for immune- and tumor damage-associated response with Lattice SBRT
 

Endpoints:	
Primary:
 
 
1. Rate of local control by RECIST at 6 months
 
2. Proportion of patients with treatment-related grade 3+ CTCAE v5.0 toxicity assessed within 6 months of completion of treatment
 
 
Secondary:
 
 
1. Proportion of patients with treatment-related grade 3+ CTCAE v5.0 toxicity at 12 months.
 
2. PRO-CTCAE assessment at baseline, post-treatment, 30 days, 3 months, 6 months, and 12 months.
 
3. PROMIS physical function, global health, anxiety, and depression assessment at baseline, post-treatment, 30 days, 3 months, 6 months, and 12 months.
 
4. Numeric Pain Scale at baseline, post-treatment, 30 days, 3 months, 6 months, and 12 months.
 
 
Exploratory: Peripheral blood immune-related biomarkers.

Study Population:	67 adult patients will be enrolled and treated, (with a goal of 47 evaluable patients), $\geq 18$ years of age with ECOG $\leq 2$ . At least 10 patients will be enrolled in each cohort (soft tissue sarcomas, thoracic cancers (including esophageal), abdominal, and pelvic cancers). All genders and races will be included. Any participants who do not receive treatment will be replaced.
Phase:	N/A
Description of Sites / Facilities Enrolling:	This is a single-institutional study conducted at Washington University School of Medicine
Description of Study Intervention:	5-fraction Lattice SBRT delivered to 20 Gy with a simultaneous integrated boost (SIB) to 66.7 Gy.
Study Duration:	16 months plus 2 weeks for treatment and 12 months follow up
Participant Duration:	2 weeks of treatment plus 12 months follow up.

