**Notes:**

1. Treatment is given every other day.
2. Completed at least 2 weeks prior to treatment with Lattice SBRT.
3. Every patient will be required to have 1 on-treatment visit per standard clinical practice.
4. For women of child-bearing potential only, and within 20 days prior to study entry.
5. +/- 1 week.
6. +/- 2 weeks
7. Within the past 4 months
8. Imaging will be performed per care team. CT, MRI, or PET/CT are acceptable modalities, but it is recommended that the same method be used at all imaging timepoints.
9. Follow up will take place at 90 days, 180 days, and 360 days, +/- 4 weeks.
10. PROMIS and PRO-CTCAE will be utilized at these timepoints.
11. AEs will be tracked through 360 days post treatment.
12. Peripheral blood for immune monitoring can be collected up to 2 weeks prior to first day of treatment, but no later than 1st day of treatment.
13. Peripheral blood for immune monitoring will be collected at fraction 5 only.
14. For all patients, assessments of hematologic and metabolic function will be collected no more than 1 week before treatment (including on the day of treatment), immediately after radiotherapy completion (Fraction 5), at 48-72 hours after radiotherapy completion, and 7 days (+/- 1 day) after radiotherapy completion. This must include assessments of uric acid, potassium, phosphorus, and calcium.

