## 2.0 OBJECTIVES AND ENDPOINTS

Objectives	Endpoints	Justification for Endpoints
Primary		
To evaluate the efficacy of 5-fraction palliative Lattice SBRT in patients with large lesions who are planning to undergo palliative radiotherapy ( $\geq 4.5$ cm).	Rate of target lesion local control at 6 months per RECIST 1.1	RECIST 1.1 is a standard measure of local control.
To evaluate the acute and sub-acute toxicity of 5-fraction palliative Lattice SBRT in patients with large lesions who are planning to undergo palliative radiotherapy ( $\geq 4.5$ cm).	Rate treatment-related, non-hematologic CTCAE v5.0 Grade $\geq 3$ toxicity at 6 months	SBRT to large tumors is traditionally associated with high dose to OARs, with sequelae of radiation-induced toxicities. As these patients have no effective treatment options, evaluation of the safety of this method of dose-

		escalation with SBRT is warranted. CTCAE v5.0 is a widely accepted standardized measure of treatment-related toxicity.
Secondary		
To assess pain response to Lattice SBRT	For patients that have pain, their pain level will be assessed with the pain Numeric Rating Scale (NRS)	The NRS is an 11-point scale for patient self-reporting of pain. This is selected because it is a reliable and clinically meaningful measure of pain that is extensively used in research and clinical practice.
To assess patient-reported toxicity outcomes	For patients that do not have pain, patient-reported symptom response will be assessed with PRO-CTCAE. A treatment site specific package of PRO-CTCAE measures will be defined for each treatment location (thorax, abdomen, pelvis, extremity)	PRO-CTCAE is a standardized inventory to collected patient reported symptomatic adverse events in clinical trials.
To assess patient reported quality of life outcomes	Patient reported quality of life and functional outcomes will be measured before treatment, after treatment, and at each follow up with the PROMIS Global, Physical Function, Pain Interference, Anxiety, and Depression system	This patient reported outcome inventory was selected because it is a reliable and clinically meaningful measure of patient reported toxicities and functional outcomes.
Exploratory		

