## **5.8 Definitions of Evaluability**

All patients enrolled on the study are evaluable for toxicity if they have received at least one fraction of radiation. Patients are evaluated from first receiving study treatment until 90 days after the conclusion of treatment or death. Participants who are consented but do not receive study treatment will be replaced.

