## **7.0 REGULATORY AND REPORTING REQUIREMENTS**

The entities providing oversight of safety and compliance with the protocol require reporting as outlined below. Please refer to Appendix B for definitions and Appendix C for a grid of reporting timelines.

Adverse events will be tracked from start of treatment through 360 days following the completion of radiotherapy. All adverse events must be recorded on the toxicity tracking case report form (CRF) with the exception of:

- Baseline adverse events, which shall be recorded on the medical history CRF
- AEs that do not fall under the following categories
  - Gastrointestinal
  - Hepatobiliary
  - Immune system
  - Metabolic
  - Nervous system
  - Renal and urinary
  - Respiratory
  - Skin disorders
- AEs that are grade 1

Refer to the data submission schedule in Section 9.1 for instructions on the collection of AEs in the EDC.

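### The 12-month toxicity objective is labelled late toxicity but contains the whole 6-month co-primary, and the 90-day limit in section 5.8 contradicts the follow-up that both endpoints need

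*Combined protocol and SAP*

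**What the plan says.** The Protocol Summary pairs two toxicity endpoints of the same grade and attribution. The co-primary is "Proportion of patients with treatment-related grade 3+ CTCAE v5.0 toxicity assessed within 6 months of completion of treatment". The first secondary objective is "To assess the rate of treatment-related severe toxicity within 12 months of completion of treatment (i.e. late toxicity", and its endpoint line reads "Proportion of patients with treatment-related grade 3+ CTCAE v5.0 toxicity at 12 months".

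The table in section 2.0 gives the 6-month endpoint this purpose: "To evaluate the acute and sub-acute toxicity of 5-fraction palliative Lattice SBRT in patients with large lesions". It also limits that endpoint to non-hematologic events. The 12-month toxicity objective does not appear in that table. Section 11.2 does not mention it either, since the secondary endpoints discussed there are all patient-reported. Section 11.3 offers only descriptive statistics for toxicity. No section names a day after which toxicity counts as late.

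On the observation period, section 5.8 says "Patients are evaluated from first receiving study treatment until 90 days after the conclusion of treatment or death". Section 7.0 says "Adverse events will be tracked from start of treatment through 360 days following the completion of radiotherapy", and note 11 to the Schedule of Activities says "AEs will be tracked through 360 days post treatment". Section 5.1 plans toxicity evaluation at 30 days and at 3, 6 and 12 months. Section 5.12 sets follow-up at 14, 30, 90, 180 and 360 days.

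**The concern.** There are two problems.

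**The label does not fit the measure.** A patient with one grade 3 event at day 20 that resolves enters the 6-month co-primary as acute toxicity and then enters the 12-month figure, where the objective calls it late. A reader who takes the label at face value could mistake early harm for delayed harm. With a high-dose boost, delayed harm is a question the trial will be asked to answer.

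**The observation windows conflict.** Section 5.8 is the plan's definition of evaluability for toxicity. An analyst who applies it as written stops counting at day 90. That affects more than the secondary endpoint, because the co-primary runs to 6 months and section 11.2 judges the treatment safe if the grade 3+ rate is below 20%. The 5.8 window would lower the rate compared with that limit by leaving out treatment-related events in months 4 to 6.

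**Working it through.** **The plan's own figure.** The plan states no number for late toxicity. Its only sample-size figure concerns local control: 47 evaluable patients for a 95% interval of ±15%, and 67 enrolled at up to 30% loss (11.2, 11.4). It reproduces. The exact interval for 23/47 is 34.1% to 63.9%, a half-width of 14.9%, and 47/0.7 = 67.1. What follows does not depend on it.

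**Step 1: containment.** Let A be the patients with a treatment-related grade 3+ event within 6 months of completion, and B those with one within 12 months. Every patient in A is in B. Hence |B|/N ≥ |A|/N for the same N patients, with equality when no new patient has an event after month 6. The non-hematologic restriction in 2.0 can only make A smaller, so containment still holds.

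**Step 2: how much of the labelled figure is early toxicity.** Inputs:
- e, the share with an event by 6 months: assumed over 5–25%, the grade 3+ range cited in 11.2 (no time window is given there).
- l, the share with an event between months 6 and 12: not in the documents, assumed at 0%, 5% and 10%.
- N = 67, with full follow-up, and early and late events independent.

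Formula: 12-month proportion = e + (1 − e) × l. Early share = e divided by that proportion.

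| e | l = 0% | l = 5% | l = 10% |
|---|---|---|---|
| 5% | 5.0% (all early) | 9.75% (51% early) | 14.5% (34% early) |
| 15% | 15.0% (all early) | 19.25% (78% early) | 23.5% (64% early) |
| 25% | 25.0% (all early) | 28.75% (87% early) | 32.5% (77% early) |

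Worked line: 0.15 + 0.85 × 0.05 = 0.1925, or 12.9 of 67, and 0.15/0.1925 = 78%. With no late toxicity the figure still equals e. With 5–10% late toxicity, 34–87% of it comes from patients already in the co-primary.

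**Step 3: does subtraction recover the late rate?** Take assumed counts of 7 patients by month 6 and 10 by month 12. The reported figures are 7/67 = 10.4% and 10/67 = 14.9%, and 10 − 7 = 3 patients with a first event after month 6. The difference misses patients with both an early and a late event, N × e × l: from 67 × 0.05 × 0.05 = 0.2 to 67 × 0.25 × 0.10 = 1.7 patients. It would miss more if an early severe event makes a late one likelier. Its denominator also keeps patients who died before the late period began.

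**Step 4: the 5.8 window.**
- Share of the co-primary window lost: (180 − 90)/180 = 50%.
- Share of the 12-month window lost: (360 − 90)/360 = 75%.

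**The case against.** The best defence is that a cumulative 12-month proportion is a legitimate measure and that only the label is wrong. The same proportion is reported at 6 and 12 months, so the increment shows first events after month 6. This largely stands: Step 3 puts the patients missed at about 0.2 to 1.7 of 67. It does not rescue the label, and the plan nowhere says that the increment is the late-toxicity result.

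Four stronger readings are tempting, and the documents do not support them.
- *The trial cannot measure late toxicity, or the endpoint merely repeats the co-primary.* The endpoint is a proportion of patients to which first events in months 6–12 are added, and adverse events are tracked to 360 days. It exceeds zero without late events only if at least one patient had an early one.
- *Events after day 90 are lost.* Sections 7.0 and 9.1 require recording beyond that day, apart from the exceptions listed in 7.0, and section 9.0 makes the Toxicity Form continuous. Section 5.8 is one sentence against several, so this is a contradiction to reconcile and not evidence that collection stops.
- *The endpoint line means prevalence at the 12-month visit.* The wording alone allows it. But the co-primary is written as *within* 6 months in the Summary and *at* 6 months in 2.0, so the plan uses the two interchangeably, and the paired objective says *within*.
- *47 patients would be at risk for late toxicity.* That is the number expected to be evaluable for local control at 6 months. Under 5.12 a patient without a 6-month scan can still be followed by phone or records, so the documents give no figure for the late at-risk group.

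**Conclusion.** The point holds as a definition error in a named safety objective, plus a separate internal contradiction on the toxicity window. Both should be corrected.

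Containment follows from the wording and needs no assumption beyond counting the same patients. The 34–87% early share rests on the cited 5–25% range, an assumed 5–10% late rate, independence and full follow-up, so it illustrates scale and predicts nothing. The 50% and 75% losses under 5.8 are arithmetic on the stated days and apply only if that sentence is followed literally.

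The mislabelling affects a descriptive secondary endpoint. The 5.8 conflict is the more consequential part, because it also reaches the co-primary.

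**What to change.** 1. In the Protocol Summary, name the present measure *cumulative 12-month grade 3+ treatment-related toxicity*, in the objective and in the endpoint line.
2. Report late toxicity separately: the proportion of patients with a treatment-related grade 3+ event with onset after day 180 and up to day 360, among treated patients alive and in toxicity follow-up at day 180. Day 180 follows from the plan's own assignment of the first 6 months to acute and sub-acute toxicity.
3. State how death or loss between days 180 and 360 is handled, for example by treating death as a competing event and reporting the number lost. State also that a severe event starting before day 180 and persisting past it stays in the cumulative figure only.
4. Add the objective to the table in 2.0 and to 11.2.
5. Reconcile 5.8 with 5.1, 5.12, 7.0 and schedule note 11, so that the toxicity evaluation window covers both the 6-month co-primary and the 12-month secondary endpoint.

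The changes are to wording only. Tracking to 360 days is already planned, so the one data need is an onset date for each event. The price is a smaller denominator, and so a wider interval, for the late rate.

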## SCHEMA

## SCHEDULE OF ACTIVITIES

Procedures	Screening	Pre-Tx / Baseline	Fractions 1-5	EOT (2 Weeks Post-Tx) 	30 Days Post-Tx 	Follow-Up 
Informed consent	X					
Demographics	X					
ECOG PS	X					
Physical exam (including ht/wt)	X		X 		X	
Medical history	X					
Pregnancy test 	X					
TLS risk designation		X				
Hematology and metabolic function	X	X 	X 	X 		
Staging of the chest, abdomen, and pelvis 		X 				X
Peripheral blood collection		X 	X 	X	X	
Questionnaires 		X 		X	X	X
Lattice SBRT 			X			
AE review and evaluation		X	X 		X	X 

**Notes:**

1. Treatment is given every other day.
2. Completed at least 2 weeks prior to treatment with Lattice SBRT.
3. Every patient will be required to have 1 on-treatment visit per standard clinical practice.
4. For women of child-bearing potential only, and within 20 days prior to study entry.
5. +/- 1 week.
6. +/- 2 weeks
7. Within the past 4 months
8. Imaging will be performed per care team. CT, MRI, or PET/CT are acceptable modalities, but it is recommended that the same method be used at all imaging timepoints.
9. Follow up will take place at 90 days, 180 days, and 360 days, +/- 4 weeks.
10. PROMIS and PRO-CTCAE will be utilized at these timepoints.
11. AEs will be tracked through 360 days post treatment.
12. Peripheral blood for immune monitoring can be collected up to 2 weeks prior to first day of treatment, but no later than 1st day of treatment.
13. Peripheral blood for immune monitoring will be collected at fraction 5 only.
14. For all patients, assessments of hematologic and metabolic function will be collected no more than 1 week before treatment (including on the day of treatment), immediately after radiotherapy completion (Fraction 5), at 48-72 hours after radiotherapy completion, and 7 days (+/- 1 day) after radiotherapy completion. This must include assessments of uric acid, potassium, phosphorus, and calcium.

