## 3.0 STUDY POPULATION

### 3.1 Inclusion Criteria

1. Histologically or cytologically confirmed sarcoma (including extremity), thoracic cancer (including esophageal), abdominal cancer, or pelvic cancer.

2. Planning to undergo palliative radiotherapy to a lesion  $\geq$  4.5 cm as measured with radiographic imaging or with calipers by clinical exam.
3. ECOG performance status  $\leq$  2
4. At least 18 years of age.
5. Radiotherapy is known to be teratogenic. For this reason, women of childbearing potential and men must agree to use adequate contraception (hormonal or barrier method of birth control, abstinence) prior to study entry and for the duration of study participation. Should a woman become pregnant or suspect she is pregnant while participating in this study, she must inform her treating physician immediately. Men treated or enrolled on this protocol must also agree to use adequate contraception prior to the study, for the duration of the study, and 6 months after completion of the study
6. Ability to understand and willingness to sign an IRB approved written informed consent document.

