### **3.2 Exclusion Criteria**

1. Prior high-dose radiotherapy that overlaps with any planned site of protocol radiotherapy. Patients where the Lattice SBRT fields may overlap with the low dose ( $<10$  Gy) region of prior radiotherapy treatments are eligible and may be treated if this is determined to be safe by the treating physician.
2. Patients with tumors in need of urgent surgical intervention, such as life-threatening bleeding or those at high risk for pathologic fracture.
3. Currently receiving any cytotoxic cancer therapy regimens or VEGF inhibitors that will overlap with the Lattice SBRT administration.
  - a. Cytotoxic chemotherapy and VEGF inhibitors prior to radiotherapy or planned after radiotherapy delivery are allowed at the discretion of the treating radiation oncologist. This includes continuing a treatment plan which was initiated prior to the start of radiotherapy. A 2-week washout is recommended, but not required.
4. Pregnant. Women of childbearing potential must have a negative pregnancy test within 20 days of study entry.
5. Patients with HIV are eligible unless their CD4+ T-cell counts are  $< 350$  cells/ $\mu$ L or they have a history of AIDS-defining opportunistic infection within the 12 months prior to registration. Concurrent treatment with effective ART according to DHHS treatment guidelines is recommended. Recommend exclusion of specific ART agents based on predicted drug-drug interactions (i.e. for sensitive CYP3A4 substrates, concurrent strong CYP3A4 inhibitors (ritonavir and cobicistat) or inducers (efavirenz) should be contraindicated).

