## 9.0 DATA SUBMISSION SCHEDULE

Case report forms with appropriate source documentation will be completed according to the schedule listed in this section.

Case Report Form	Submission Schedule
Original Consent Form	Prior to registration
On-Study Form Medical History Form	Prior to starting treatment
Specimen Collection Form	Screening, immediately after radiotherapy completion (Fraction 5), 14 days after radiotherapy, and 30 days after radiotherapy
Questionnaires	Baseline, after radiation at 2 weeks, 1 month, 3 months, 6 months, and 1 year
Toxicity Form	Continuous
Treatment Summary Form	Completion of treatment
RECIST Form	Baseline, then 3 months, 6 months, and 1 year post treatment
Follow Up Form	After radiation at 2 weeks, 1 month, 3 months, 6 months, and 1 year
Death Form	At time of death (if applicable)

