### 11.2 Study Endpoints

The co-primary endpoints are rate of local control of the treated (i.e. target) lesion at 6 months, and proportion of patients with treatment related grade 3+ CTCAE v5.0 toxicity. Local control will be determined by RECIST 1.1 analysis of baseline compared with imaging at 6 months. Imaging may include CT scan, PET/CT, or MRI. It is strongly suggested that the same imaging modality is used between baseline and at every follow-up timepoint for staging of disease.

Importantly, there are limited available data to determine expected local control of large tumors after SBRT. Almost all studies have focused on tumors with average maximal diameter of only 5.5 cm corresponding to a tumor volume of approximately 87 cc. In such studies, local control rates are approximately 70-85%. In the pilot study of Lattice SBRT at Washington University, the median treated tumor volume was 435 cc (N=14). Likewise, these few studies of SBRT for large tumors report a grade 3+ toxicity rate of 5-25%, varying based on tumor location.

Due to the lack of a reliable historical comparison, the enrollment target was defined by clinical considerations as opposed to power calculations for comparison with a historical control. This study instead seeks to establish the expected local control rate at 6 months for patients with such large tumors treated with Lattice SBRT. After discussing with internal and external stakeholders, we determined that a clinically reasonable bound on local control at 6 months would be 15%. Approximately 47 patients would be required to determine local control with a 95% confidence interval of +/- 15%; 67 patients will be enrolled to get 47 evaluable patients. We anticipate that up to 30% of patients may not be evaluable for local control at 6 months and are accounting for this potential drop-out rate by enrolling 67 patients. This is because patients with very large tumors needing palliative radiotherapy often have short survival.

Likewise, the study seeks to establish the expected grade 3+ treatment related toxicity rate for treatment of large tumors with lattice SBRT. The treatment will be considered safe if the grade 3+ treatment related toxicity rate is less than 20%, which is in line with prior studies of SBRT of large tumors.

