### **11.3 Data Analysis**

Demographic and clinical characteristics including treatment toxicity will be summarized using descriptive statistics. RECIST 1.1 will be used to determine local control per the protocol described in Appendix E. The RCI will be used to compare the QoL scores between before and after treatment with Lattice SBRT.

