#### **Methods for Evaluation of Measurable Disease**

All measurements should be taken and recorded in metric notation using a ruler or calipers. All baseline evaluations should be performed as closely as possible to the beginning of treatment and never more than 4 weeks before the beginning of the treatment.

The same method of assessment and the same technique should be used to characterize each identified and reported lesion at baseline and during follow-up. Imaging-based evaluation is preferred to evaluation by clinical examination unless the lesion(s) being followed cannot be imaged but are assessable by clinical exam.

**Clinical lesions:** Clinical lesions will only be considered measurable when they are superficial (e.g., skin nodules and palpable lymph nodes) and  $\geq 10$  mm diameter as assessed using calipers (e.g., skin nodules). In the case of skin lesions, documentation by color photography, including a ruler to estimate the size of the lesion, is recommended.

**Chest x-ray:** Lesions on chest x-ray are acceptable as measurable lesions when they are clearly defined and surrounded by aerated lung. However, CT is preferable.

**Conventional CT and MRI:** This guideline has defined measurability of lesions on CT scan based on the assumption that CT slice thickness is 5 mm or less. If CT scans have slice thickness greater than 5 mm, the minimum size for a measurable lesion should be twice the slice thickness. MRI is also acceptable in certain situations (e.g. for body scans).

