## Response Criteria

### Evaluation of Target Lesions

**Complete Response (CR):** Disappearance of all target lesions. Any pathological lymph nodes (whether target or non-target) must have reduction in short axis to <10 mm.

**Partial Response (PR):** At least a 30% decrease in the sum of the diameters of target lesions, taking as reference the baseline sum diameters.

**Progressive Disease (PD):** At least a 20% increase in the sum of the diameters of target lesions, taking as reference the smallest sum on study (this includes the baseline sum if that is the smallest on study). In addition to the relative increase of 20%, the sum must also demonstrate an absolute increase of at least 5 mm. (Note: the appearance of one or more new lesions is also considered progressions).

**Stable Disease (SD):** Neither sufficient shrinkage to qualify for PR nor sufficient increase to qualify for PD, taking as reference the smallest sum diameters while on study.

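### The Schedule accepts a baseline scan up to 4 months old, Appendix E allows at most 4 weeks, and no section names the RECIST baseline scan for the co-primary local control endpoint

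*Combined protocol and SAP*

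**What the plan says.** The Schedule of Activities has a single imaging row, for staging of the chest, abdomen and pelvis. Its only pre-treatment entry sits in the Pre-Tx / Baseline column and carries Note 7: "Within the past 4 months". The note does not say whether the 4 months run back from consent, registration or the first fraction. Note 8 leaves imaging to the care team. Section 5.4 lists the same imaging with no window.

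Appendix E (Methods for Evaluation of Measurable Disease) says baseline evaluations should be as close as possible to the start of treatment and "never more than 4 weeks before the beginning of the treatment". Section 11.3 makes that appendix binding for the endpoint: "RECIST 1.1 will be used to determine local control per the protocol described in Appendix E".

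Section 11.2 defines how the baseline is used: "Local control will be determined by RECIST 1.1 analysis of baseline compared with imaging at 6 months". Section 9.0 sets the RECIST form's due dates as "Baseline, then 3 months, 6 months, and 1 year post treatment". Appendix E has the treated lesions measured at baseline. None of these identifies the scan.

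Section 5.5.1 requires a planning CT or MRI, for the stated purpose of defining the PTV. It does not date that scan relative to the first fraction or give it a role in response assessment.

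**The concern.** Staff who follow the Schedule can meet every requirement in it and still have no baseline that Appendix E accepts. Local control is a co-primary endpoint of a study with no control arm, so any change in the lesion between an old scan and the first fraction is read as an effect of treatment. The error can go either way:

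- **False progression.** Growth before treatment counts towards the 20% threshold. If no on-study scan falls below the old measurement, a lesion that is at least 1.2 times that measurement at 6 months is called progressive, even if it barely changed after radiotherapy.
- **False control.** Section 3.2 states: "Cytotoxic chemotherapy and VEGF inhibitors prior to radiotherapy or planned after radiotherapy delivery are allowed at the discretion of the treating radiation oncologist". Shrinkage from such earlier therapy, if it falls between the old scan and the first fraction, can be credited to Lattice SBRT.

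There is also a coverage gap. Section 3.1 admits extremity sarcoma, and a chest, abdomen and pelvis scan need not image that target at all.

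**Working it through.** **The plan's own figure.** Sections 11.2 and 11.4 give 47 evaluable patients for a 95% interval of ±15 points. This reproduces with exact (Clopper-Pearson) limits near 50%: the half-width is 0.151 at 23/46 and 0.149 at 23/47. With 67 enrolled and 30% lost, 67 × 0.70 = 46.9. The finding does not depend on these numbers; they only set the scale.

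**The windows side by side**, taking 4 months as about 120 days:

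| Scan age before treatment | Note 7 | Appendix E |
|---|---|---|
| 0 to 28 days | met | met |
| 29 to about 120 days | met | breached |

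120 / 28 = 4.3, so the Schedule's window is more than four times the appendix's.

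**How much a lesion could change (illustration).** The documents give no growth rate and no scan ages. Assume exponential growth of a sphere with volume doubling time VDT and scan age t, both in days. Then:

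- Diameter growth before treatment = 2^(t / (3 × VDT)) − 1
- Longest VDT at which growth reaches 20% = t × ln 2 / (3 × ln 1.2)
- Scan age at which growth reaches 20% = 3 × VDT × ln 1.2 / ln 2

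| Assumed VDT (days) | Growth, t = 28 | Growth, t = 120 | Scan age at +20% (days) |
|---|---|---|---|
| 90 | 7.5% | 36.1% | 71.0 |
| 120 | 5.5% | 26.0% | 94.7 |
| 180 | 3.7% | 16.7% | 142.0 |
| 365 | 1.8% | 7.9% | 288.0 |

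Growth before treatment alone reaches 20% when VDT is at most 152.1 days for t = 120, against 35.5 days for t = 28. At VDT 180 or 365 it does not reach 20% inside 4 months. The 5 mm absolute requirement gives little protection at this size: 20% of 45 mm is 9 mm.

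**Dilution.** Appendix E sums the diameters of all treated lesions. If only one of two equal lesions grows, 26.0% becomes 26.0 / 2 = 13.0% in the sum.

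**Opposite direction.** If the lesion shrank by a fraction s between the old scan and the first fraction, it can regrow 1.2 / (1 − s) − 1 from its true size before reaching +20% of the old diameter. For an assumed s = 0.10 this is 33.3%; for s = 0.20 it is 50.0%.

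**Reset.** Appendix E measures progression from the smallest sum on study. A later scan that falls below the old baseline replaces it as the reference, which removes the error in that patient.

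**Effect on the estimate.** Each misclassified patient moves the local control rate by 1 / 47 = 2.1 percentage points.

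**The case against.** The best defence is that the plan already contains the governing rule. Note 7 is attached to a staging row; Appendix E sets a specific limit for baseline evaluations, and Section 11.3 makes it the endpoint method. On that reading, using a 3-month-old scan for RECIST is a deviation that the plan does not permit. In addition, every patient has a planning scan, Appendix E defines target lesions as the contoured GTVs, and the planning scan must cover an extremity target. Section 3.1 also accepts caliper measurement for eligibility.

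This shows that a compliant baseline is obtainable, but no section says that Note 7 is for staging only. The Pre-Tx / Baseline column heading, and the advice in Section 11.2 to keep one modality from baseline through follow-up staging, point towards the staging scan as the baseline. The planning scan has no stated timing or endpoint role, and Section 6.0 allows an existing plan to be used after a delayed start of any length.

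The second objection is that the growth figures are hypothetical, use the oldest permitted scan and leave out treatment effect. This stands. Under the same model, a lesion at +26% escapes a progression call if it shrinks about 5% after treatment (1 − 1.2 / 1.26), and one at +36.1% if it shrinks about 12% (1 − 1.2 / 1.361). The number of patients affected is unknown.

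**Conclusion.** The inconsistency is real and can be verified from the text alone. A scan 29 to about 120 days old is acceptable under the Schedule and unacceptable under the rule for a co-primary endpoint, and the baseline scan is never named. The resulting bias has no fixed direction and no computable size. The 152-day and 35-day doubling times rest on assumed exponential spherical growth and show only that the longer window makes misclassification plausible at much slower growth. The effect is smaller or absent with slow growth, with several target lesions, with enough shrinkage after treatment, or where a later scan resets the reference. At 2.1 points per patient, a few cases would be noticeable against a 15-point half-width: three would be 3 / 47 = 6.4 points. The point should be corrected; it does not affect the sample size.

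**What to change.** Reconcile Note 7 with Appendix E:

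- State that the RECIST baseline for the target lesion must be obtained no more than 4 weeks before the first fraction, which is the plan's own limit, and name the scan (or caliper measurement) that supplies it.
- Keep the 4-month allowance for staging of other sites only.
- Where the staging scan is older or does not cover the target, measure the lesion on the planning CT or MRI required by Section 5.5.1, subject to the same 4-week limit. The limit must be written out, because Section 6.0 permits existing plans after a delay.
- Record baseline scan date and modality on the RECIST form, if it does not already capture them.
- Report a sensitivity analysis for patients whose baseline was older than 4 weeks, or whose baseline and follow-up techniques differ.

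The cost is one wording change, up to two form fields, one measurement on a scan already required, and one analysis. Repeat imaging is needed only when both the staging and planning scans are too old or the only recent one does not show the target. The drawback is that a planning scan may differ in contrast or technique from follow-up imaging, while Appendix E asks for the same technique throughout; the sensitivity analysis covers this. For patients already treated, scan dates can be recorded and the same analysis run.
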